While the study design of this proposed phase Ib/Ila clinical trial is based on Koreth *et al*'s study, patients with active UC are likely to be fitter than patients with steroid-resistant GvHD following BMT. In a recent study with a more comparable group, Saadoun *et al*.⁵² treated 10 patients with HCV-associated vasculitis that was unresponsive to conventional anti-viral therapy and/or rituximab with low-dose IL-2: 1.5 MIU/day for 5 days, followed by three 5-day courses of 3 MIU/day at weeks 3, 6 and 9. Only mild (grade 1) toxicities were observed, including fatigue (4/10), flu-like symptoms (4/10), SC injection site reaction (2/10), arterial hypertension (1/10) and myalgia (1/10).

4.7 Hypothesis.

Based on these data, we hypothesize that low-dose IL-2 will safely expand PB and LP Tregs *in vivo* in patients with UC and be efficacious in controlling disease.

5 STUDY DESIGN AND OBJECTIVES.

5.1 Study Design.

An open-label, phase Ib/IIa clinical trial, with a 3+3 dose escalation design, to determine the safety and the maximum tolerated dose (MTD) of daily SC recombinant human interleukin-2 (IL-2, aldesleukin, Proleukin®) in adult subjects with moderate to severe UC.

5.2 Primary Objectives.

- (i). To determine the safety of daily SC low dose IL-2 in subjects with moderate to severe UC
- (ii). To determine the MTD of daily SC low dose IL-2 in subjects with moderate to severe UC.

5.3 Secondary Objectives.

- (i). To determine the feasibility of administering an eight week course of daily SC low dose IL-2 to subjects with moderate-to-severe UC.
- (ii). To determine the clinical response to the above treatment.
- (iii). To assess the immunological response to the above treatment, with particular reference to numbers and function of T_{regs} in the blood and intestinal lamina propria (LP)

6 SUBJECT SELECTION.

6.1 Inclusion Criteria.

- (i). Age 18-70 years. Maximum age limit for subjects recruited at BCH will be 30 years.
- (ii). A diagnosis of UC made by standard clinical, radiological, endoscopic and histological criteria.
- (iii). Moderate to severe UC with a Mayo score of 6-12.

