Assessments after week 1 (as indicated in Table 3, page 37) will be scheduled for the planned day ± 3 days. Tests that would be performed as part of routine clinical care are highlighted as follows: “(routine)”.

11.1 Screening (Pre-Treatment) Evaluation (Week -2).

Following signed, informed consent, the following screening evaluation will be performed within two weeks of the anticipated start date of aldesleukin therapy:

- Medical history including confirmation of fulfillment of inclusion criteria (routine).
- Physical examination, including vital signs, weight, height (routine).
- Pregnancy test for women of childbearing potential.
- Screening test for tuberculosis (TB): IFN- γ Release Assay (IGRA), e.g. QuantiFERON®. If the IGRA result is “indeterminate” or “positive”, a CXR will be performed as part of routine clinical care to exclude pulmonary TB.
- Stool for culture and sensitivity (C&S), ova and parasites (O&P), *Clostridium difficile* stool toxin and fecal calprotectin (routine).
- Flexible sigmoidoscopy and biopsies with calculation of the Mayo score; or colonoscopy and biopsies if the subject has never had a full colonoscopy (routine). As part of routine clinical evaluation, two biopsies will be obtained when possible from each of the following sites: rectum, sigmoid colon, descending colon (n=up to 6). In addition, biopsies for research will be obtained from each site. From the descending colon, biopsies will be obtained to characterize lamina propria immune cells on fresh cells by flow cytometry

(n=2), transcriptomics (n=1), and for deeper immunologic and single cell analysis (n=5). From the sigmoid colon, biopsies will be obtained to characterize LPMCs on fresh cells by flow cytometry (n=2), transcriptomics (n=1), to cryomold for histologic assessment (n=2), and for deeper immunologic and single cell analysis (n=5). From the rectum, biopsies will be obtained to characterize LPMCs on fresh cells by flow cytometry (n=2), transcriptomics (n=1), mucosal microbiota (n=2), to cryomold for histologic assessment (n=2), and for deeper immunologic and single cell analysis (n=5).

- Hematology: Complete blood count (CBC) and differential (routine).
- Inflammatory markers: ESR and CRP (routine).
- Serum chemistries: glucose, BUN, creatinine, uric acid, total bilirubin, alkaline phosphatase, LDH, total protein, albumin, AST, ALT, and calcium (routine).
- Thyroid function tests (TSH, T3, free T4) (routine).
- Virology: serology for HIV, HBV and HCV.

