Note: The following basic science investigations can be performed at the screening visit or at the baseline (Day 0) visit, at the discretion of the investigator.

- Immunology bloods: Quantitative flow cytometric assessment of leucocytes, NK cells and Treg subsets from PB and endoscopic biopsies. Assessment of PB and LP Treg function. Banking of PBMCs, plasma, RNA, DNA.
- Microbiology: Stool sample and mucosal biopsies for analysis of the intestinal microbiome.
- IL-2 serum levels and anti-aldesleukin antibodies.

11.2 Baseline, Treatment and End-of-Study Evaluations (Day 0 to Week 6 and Week 12).

The following evaluations will be performed at baseline (day 0), day 4 (optional visit), and weeks 1, 2, 4, 6 and 12:

- Medical history and physical examination, including assessment of symptoms and signs in order to detect potential drug toxicity (routine).
- Hematology: Complete blood count (CBC) and differential (routine).
- Inflammatory markers: ESR and CRP (routine).
- Serum chemistries: glucose, BUN, creatinine, uric acid, total bilirubin, alkaline phosphatase, LDH, total protein, albumin, AST, ALT, and calcium (routine).
- Thyroid function tests (TSH, T3, free T4) (week 12).
- Immunology bloods: Quantitative flow cytometric assessment of leucocytes, NK cells and Treg subsets from PB. Assessment of PB and LP Treg function. Banking of PBMCs, plasma, RNA, DNA.
- Microbiology: Stool sample for analysis of the intestinal microbiome (day 0, weeks 1, 2, 4, 6, 8 and 12).
- Fecal calprotectin (day 0, weeks 1, 2, 4, 6, 8 and 12).
- IL-2 serum levels and anti-aldesleukin antibodies (not days 1 or 4).

Participants will attend the CTSU for their first IL-2 dose on day 0 and their second IL-2 injection on day 1. Participants will be evaluated clinically at that encounter.

11.3 End of Treatment Evaluation (Week 8).

The following evaluations will be performed at week 8:

- Medical history and physical examination, including assessment of symptoms and signs in order to detect potential drug toxicity (routine).
- Flexible sigmoidoscopy and biopsies with calculation of the Mayo score. The same biopsies will be obtained as at the screening procedure, except that histology will be limited to the rectum and sigmoid/distal descending colon.
- Hematology: Complete blood count (CBC) and differential (routine).

- Inflammatory markers: ESR and CRP (routine).

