A Data Safety and Monitoring Board (DSMB) has been constituted. The DSMB members are as follows: [name] MD PhD (Chair, Gastroenterologist, University of North Carolina at Chapel Hill), [name] MB BS MPH (Gastroenterologist, Massachusetts General Hospital), and [name] PhD (Statistician, Boston Children's Hospital). The DSMB will determine stopping points for individual subjects and the study as a whole. In addition, the DSMB will determine the schedule of meetings in order to review subject safety information and will also make recommendations concerning the continuation, modification or termination of the study.

The DSMB will review study data and make recommendations on the conduct of the study at the following time points:

- In the event of any serious adverse events or DLT.
- When the third subject completes 8 weeks of IL-2 treatment, as per protocol.
- Three months after study initiation.
- Six months after study initiation.
- At six month intervals thereafter.

14 STUDY ENDPOINTS.

Subjects will be periodically assessed as described in Section 11 (page 31) in order to determine if the primary and secondary endpoints have been met.

14.1 Determination of Safety of Daily SC Low Dose IL-2.

The safety of daily low-dose IL-2 will be determined by assessing for potential side-effects and dose limiting toxicity at each study visit.

14.2 Determination of the Maximum Tolerated Dose of Daily SC Low Dose IL-2.

The MTD will be determined using the dose escalation strategy and assessments described in Sections 9 and 11 (pages 21 and 31, respectively).

14.3 Determination of the Feasibility of Administering an Eight Week Course of Daily SC Low Dose IL-2 in Subjects with Moderate to Severe UC.

This relates to the technical feasibility of administering daily low-dose SC IL-2 as per protocol. The narrative report of this outcome will include the numbers of subjects enrolled, subjects who completed the protocol and a description of any barriers to the technical feasibility of this approach in subjects with UC.

14.4 Determination of the Clinical Response to Daily SC Low Dose IL-2.

Mayo score^{7,55} (Table 5; page 44) will be assessed as per protocol between weeks -2 and 0 (as close to week 0 as possible) and week 8 in order to determine clinical response. Moderate to severe UC, denoted by a Mayo score of 6-12 is an inclusion criterion. Clinical response and remission are defined according to Rutgeerts *et al.*⁷

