14.4.1 Definition of Clinical Response.

“A decrease from baseline in the total Mayo score of at least 3 points and at least 30% , with an accompanying decrease in the subscore for rectal bleeding of at least 1 point or an absolute subscore for rectal bleeding of 0 or 1.”⁷

14.4.2 Definition of Remission..

“A total Mayo score of 2 points or lower, with no individual subscore exceeding 1 point.”⁷

14.4.3 Definition of Mucosal Healing.

“An absolute subscore for endoscopy of 0 or 1.”⁷

14.5 Assessment of the Immunological Response to IL-2 Therapy.

Data obtained from research laboratory-based assessment of subject immune responses to IL-2 therapy, that do not have direct clinical relevance, will be reported as appropriate for each data type.

Table 5: Mayo Scoring System for Assessment of Ulcerative Colitis Activity.^{7,55}

Stool frequency*	
0	Normal no. of stools for this subject
1	1 to 2 stools more than normal
2	3 to 4 stools more than normal
3	5 or more stools more than normal
Rectal bleeding**	
0	No blood seen
1	Streaks of blood with stool less than half the time
2	Obvious blood with stool most of the time
3	Blood alone passes
Findings on endoscopy	
0	Normal or inactive disease
1	Mild disease (erythema, decreased vascular pattern, mild friability) ^[1,2]
2	Moderate disease (marked erythema, lack of vascular pattern, friability, erosions) ^[1,2]
3	Severe disease (spontaneous bleeding, ulceration)
Physician’s global assessment	
0	Normal
1	Mild disease
2	Moderate disease

3 Severe disease

- * Each subject serves as their own control.
- ** Represents the most severe bleeding of the day.

15 STATISTICAL CONSIDERATIONS.

The primary endpoint of this Phase I study is to determine the MTD of daily subcutaneous IL-2 in moderate to severe UC.

15.1 Probability of Dose Escalation Under Various DLT Rates.

Table 6 shows the probability of escalation under various true DLT rates. With this design, there is 91% probability of escalation if the true rate of DLT is 10% and 17% probability of escalation if the true DLT rate is 50%.

Table 6: Probability of Dose Escalation	
True rate of DLT	Probability of dose escalation
10%	0.91
20%	0.71
30%	0.49
40%	0.31
50%	0.17
60%	0.08

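### Mucosal healing (14.4.3) is an absolute endoscopy subscore of 0 or 1, but entry sets no endoscopic minimum, so a subject already at that threshold can count as healed without any change

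*Combined protocol and SAP*

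**What the plan says.** - **Endpoint.** Section 14.4.3 defines mucosal healing as "An absolute subscore for endoscopy of 0 or 1". It is quoted from the cited infliximab trial (reference 7). It names no baseline value, no required improvement and no restricted denominator.
- **Entry.** Section 6.1(iii) asks for "Moderate to severe UC with a Mayo score of 6-12", and section 14.4 repeats this: "Moderate to severe UC, denoted by a Mayo score of 6-12 is an inclusion criterion". The only inclusion criterion that mentions endoscopy is the diagnostic one, 6.1(ii): "A diagnosis of UC made by standard clinical, radiological, endoscopic and histological criteria". That concerns the diagnosis, not current endoscopic activity. The exclusion criteria in 6.2 add no endoscopic threshold.
- **Timing.** The week 8 time point comes from 14.4 and 11.3, not from 14.4.3 itself. Section 14.4 places the Mayo score between weeks −2 and 0 ("as close to week 0 as possible) and week 8 in order to determine clinical response"). Endoscopy with Mayo scoring is done at screening (11.1: "Flexible sigmoidoscopy and biopsies with calculation of the Mayo score; or colonoscopy and biopsies if the subject has never had a full colonoscopy") and at week 8 (11.3: "Flexible sigmoidoscopy and biopsies with calculation of the Mayo score"). The baseline subscore therefore exists; the definition does not use it.
- **Scale.** Table 5 labels endoscopy 0 as "Normal or inactive disease" and endoscopy 1 as mild disease.

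**The concern.** A healing rate should describe subjects whose mucosa was worse than the threshold at entry and reached it on treatment. Under 14.4.3 the numerator can also hold subjects who were at the threshold before the first dose.

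The other two efficacy definitions in 14.4 do not have this gap. Clinical response requires a fall from baseline of at least 3 points and 30%. Remission is absolute, but it needs a total of 2 or lower, which cannot coexist with entry at 6 or more.

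Mucosal healing is a named evaluation in the synopsis (3.6), and the expansion at the MTD is meant to describe efficacy as well as safety (9.3.4). At stake is how far a published healing rate from 10 to 16 subjects can be read as healing.

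**Working it through.** The plan states no healing rate, sample size or test, so there is no figure of its own to reproduce. Two checks apply.

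**1. Can an eligible subject already meet the threshold?** Inputs: four Mayo items, each 0 to 3 (Table 5), and an entry total of 6 to 12 (6.1(iii)). Of the 4 × 4 × 4 × 4 = 256 possible patterns, those with an eligible total are:

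| Baseline endoscopy | Needed from the other three items | Eligible patterns | Range of total |
|---|---|---|---|
| 0 | at least 6 | 20 | 6–9 |
| 1 | at least 5 | 32 | 6–10 |
| 2 | at least 4 | 44 | 6–11 |
| 3 | at least 3 | 54 | 6–12 |

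The eligible patterns sum to 150, of which 20 + 32 = 52 already satisfy 14.4.3. One example is stool 2, bleeding 1, global assessment 2, endoscopy 1, total 6. It fits the Appendix A description of a global score of 2 (other subscores mostly 1 to 2). Appendix A also takes the subject-reported items from the worst diary entry of the three prior days, which can raise those items but not the endoscopy item.

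**2. What does this do to the rate?** Let q be the share entering at endoscopy 0–1, s the share of those still at 0–1 at week 8, and h the share of those entering at 2–3 who reach 0–1. All three are unknown.

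- Rate under 14.4.3: qs + (1 − q)h.
- Rate among those entering at 2–3: h.
- Difference: qs + (1 − q)h − h = q(s − h).

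With s = 1 (nobody entering at 0–1 changes) and an assumed h of 20%:

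- q = 10%: 0.10 + 0.90 × 0.20 = 28%, a difference of 8 points.
- q = 20%: 0.20 + 0.80 × 0.20 = 36%, a difference of 16 points.
- q = 0: no difference.

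The sign can reverse. Suppose one of 10 subjects enters at 1 and worsens to 2, while 3 of the other 9 heal. Section 14.4.3 gives 3/10 = 30%; restricting to entry at 2–3 gives 3/9 = 33%.

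**One unchanged subject.** With k healed among the others:

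- 10 subjects (9.3.4): (k + 1)/10 − k/9 = (9 − k)/90. This is 10.0 points at k = 0, 7.8 at k = 2 and 5.6 at k = 4.
- 16 subjects (6 + 10 at the MTD, Table 1): (k + 1)/16 − k/15 = (15 − k)/240, at most 6.25 points.

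**Chance of at least one such entrant among 10**, 1 − (1 − q)^10: 40% at an assumed q of 5%, 65% at 10%, 89% at 20%.

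**The case against.** The strongest reply is that nothing is decided on this endpoint. Healing is not named in the objectives (5.2, 5.3). The MTD rule (9.4) and the extended-treatment rule (9.7) use response or remission, and section 15 plans no healing estimate. That stands, and it keeps the point minor.

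A second reply is that the definition is taken deliberately from a cited trial for comparability. This stands in part: it is a reason to keep the absolute version, but the plan does not give that trial's entry criteria, so it cannot show that the definition suits this population.

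A third is that the baseline subscore is on file, so anyone can see who entered at 0 or 1. That is true, and it makes the fix cheap, but the definition does not ask for the subscore to be used.

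Four stronger readings are tempting, and the documents do not support them:

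- *Subjects who were never endoscopically active count as healed.* Table 5 calls subscore 1 mild disease, and 32 of the 52 patterns have subscore 1. They already meet the threshold; they are not free of disease.
- *About a third of subjects are affected.* 52/150 (35%) is a share of possible score patterns, not of patients.
- *The bias can only be upward.* It is q(s − h), which is negative when s < h.
- *Each such subject adds a fixed 10 points.* Ten is the maximum, reached only when nobody else heals.

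**Conclusion.** The gap is real and minor. As written, 14.4.3 together with 6.1(iii) lets an eligible subject be counted as healed with no endoscopic change. The reported rate then departs from the rate in subjects entering at 2 or 3 by q(s − h). Upward is the likelier direction, on the assumption that a subject entering at 0–1 is more likely to be at 0–1 at week 8 than one entering at 2–3. The sizes rest on assumed values of q, s and h and on a denominator of 10 or 16, since the plan names none for healing. The number of affected subjects cannot be known from the documents and may be zero. No dose decision or primary conclusion depends on it.

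**What to change.** In 14.4.3, make the main healing rate the proportion with a week 8 endoscopy subscore of 0 or 1 among subjects whose baseline endoscopy subscore was 2 or 3. Report the number left out of the denominator. Keep the absolute definition in all subjects as a supplementary line, for comparison with the cited trial.

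This takes about a sentence of text. It needs no new procedure and no change to eligibility, because endoscopy is already scored at screening and week 8. The price is a slightly smaller denominator in an already small group, and a rate that may look less favourable.

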2/3	
Current dose level has not been tolerated. Reduce dose to the lower dose level
If only 3 subjects have been treated at the lower dose level, accrue an additional 3 subjects at the lower dose level.If 6 subjects have already been treated at the lower dose level, the lower dose level is the MTD.If this occurs at dose level A, the study will be terminated early.
1/3 + 0/3 (1/6)	
Escalate dose. Accrue 3 new subjects at next highest dose level. If 0/6 or 1/6 DLTs at dose level C, then this is the MTD.
1/3 + 1/3 (2/6)	
Current dose level has not been tolerated. Reduce the dose. If this occurs at the lowest dose level, the study will be terminated early.

To be read with reference to Section 9.3 (page 22), above. Adapted from Koreth *et al.*⁵¹

9.4 Determination of Maximum Tolerated Dose.

The maximum tolerated dose (MTD) is the highest tolerated dose level at which a minimum of 6 subjects have been evaluated, with fewer than 2 evaluable subjects in 6 experiencing a dose limiting toxicity (DLT); i.e. DLT in $\leq 1/6$ evaluable subjects. **In addition to the above, at least 1 patient should meet the criteria for response or remission for it to be considered the MTD.**

Subjects will be considered unevaluable for DLT if they are removed from the study or die without developing DLT prior to receiving at least 8 weeks of IL-2 therapy. If there are fewer than 3 evaluable subjects in a cohort, additional subjects will be added at that dose level.

Intolerable lower grade toxicity that does not meet the definition of DLT, but still means that a subject is unable to complete the per-protocol treatment will be taken as equivalent to a DLT for the purpose of assessing dose escalation. If ≥ 2 subjects in a cohort of 3 refuse to continue at that dose level for at least 8 weeks due to intolerable lower grade toxicity, that dose level will not be regarded as the MTD.

9.5 Definition of Dose Limiting Toxicities.

Organ toxicities will be assessed at scheduled clinical visits and graded according to the National Cancer Institute Common Terminology Criteria for Adverse Events v4.0⁵⁴.

- (i). **Anaphylaxis:** Life threatening anaphylaxis due to the study drug is considered a DLT.
- (ii). **Grade 4 toxicity:** Grade 4 toxicity (except colitis, see below) directly related to IL-2 by week ~~11~~8 of IL-2 treatment is considered a DLT.

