Once the MTD is established, an additional 10 evaluable subjects will be treated at the MTD level to further evaluate the toxicity as well as the feasibility. The estimation of toxicity rate will be based on these 10 additional subjects. With 10 subjects, the 90% confidence interval of the toxicity rate will be within $\pm 26\%$.

15.2 Accrual.

We anticipate that the sample size will range from 3-28 evaluable subjects, depending on number of dose levels will be tested. Based on the current practice, we anticipate that the accrual rate will be approximately 12 subjects per year, thus requiring up to 28 months to complete accrual.

16 ETHICS AND GOOD CLINICAL PRACTICE.

This study will be performed in accordance with Boston Children's Hospital's policies and guidance on the conduct of clinical research, the principles of Good Clinical Practice (GCP), the Declaration of Helsinki and applicable state and federal laws and regulations.

The study may not start without written Institutional Review Board approval and the written informed consent of the subject.

17 REFERENCES.

2. Loftus EV Jr. Clinical epidemiology of inflammatory bowel disease: incidence, prevalence, and environmental influences. *Gastroenterology* 2004;126(6):1504–17.
3. United States Census Bureau. Monthly population estimates for the United States: April 1, 2010 to May 1, 2013. (Accessed 06/17/2013.) [Internet]. www.census.gov. [cited 2013 Jun 17];Available from: <http://www.census.gov/popest/data/national/totals/2012/index.html>
5. Faubion WA Jr., Loftus EV Jr, Harmsen WS, Zinsmeister AR, Sandborn WJ. The natural history of corticosteroid therapy for inflammatory bowel disease: A population-based study. *Gastroenterology* 2001;121(2):255–60.
8. Beaugerie L. Inflammatory bowel disease therapies and cancer risk: where are we and where are we going? *Gut* 2011;

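### Does the ±26% precision figure for the toxicity rate in Section 15.1 need a named interval method?

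*Combined protocol and SAP*

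**What the plan says.** Once the MTD is fixed, Section 15.1 provides that "an additional 10 evaluable subjects will be treated at the MTD level to further evaluate the toxicity as well as the feasibility". It then says "The estimation of toxicity rate will be based on these 10 additional subjects", and adds the precision statement: "With 10 subjects, the 90% confidence interval of the toxicity rate will be within" ±26%. It gives neither an assumed rate nor an interval method.

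Section 14.1, the safety endpoint, describes assessment only: "The safety of daily low-dose IL-2 will be determined by assessing for potential side-effects and dose limiting toxicity at each study visit". No other section names a method for a binomial interval. Sections 9.3 and 9.4 set the MTD by counting DLTs (at most 1 in 6 evaluable subjects), and Section 9.4 also requires at least one responder. Neither uses a confidence interval.

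**The concern.** Safety is a primary objective, and this is the only precision statement for the only planned estimate of a toxicity rate at the MTD. The stated figure matches the Wald formula, which behaves badly with 10 subjects and few events. It gives zero width at 0/10 and negative lower limits at 1/10 and 2/10. A dose declared tolerable on at most 1 DLT in 6 is likely to produce such low counts.

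If the method is left open, it could be chosen after the counts are known. The same 0/10 could be reported with an upper limit of 0% or 26%. The ±26% claim would also be untrue if exact limits were reported. At stake is how the safety of the MTD is described.

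**Working it through.** **Inputs.** n = 10 and a 90% level, from Section 15.1. The ± sign implies a two-sided interval, so z = 1.645. No rate is given; because the text states a bound, the worst case of 50% is assumed, and every count from 0 to 10 was also checked.

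**Reproducing the plan's figure.** Wald half-width = z × √(p(1 − p)/n) = 1.645 × √(0.25/10) = 0.2601, or 26.0 points. The same formula gives 31.0 at 95% and 20.3 at 80%, so the stated 90% level is the one that fits.

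**Does the bound hold under other methods?** Largest values over 0 to 10 events, in percentage points:

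| Method | Half the total width | Distance from estimate to farther limit |
|---|---|---|
| Wald | 26.0 | 26.0 |
| Wilson | 23.1 | 25.9 |
| Exact | 27.8 | 30.7 |

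Wilson meets the bound on either reading. Exact limits break it. Measured as distance, they exceed 26 at every count from 1 to 9. Measured as half the width, they exceed it only at 4 to 6 events, by at most 27.8 − 26.0 = 1.8 points.

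**Upper 90% limits by count (%).** Three of the entries can be checked by hand:
- Wald at 1/10: 0.1 + 1.645 × √(0.09/10) = 0.256.
- Wilson at 0/10: (z²/n)/(1 + z²/n) = 0.2706/1.2706 = 0.213.
- Exact at 0/10: 1 − 0.05^(1/10) = 0.259.

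| Events of 10 | Wald | Wilson | Exact | Exact − Wald | Exact − Wilson |
|---|---|---|---|---|---|
| 0 | 0.0 | 21.3 | 25.9 | 25.9 | 4.6 |
| 1 | 25.6 | 34.8 | 39.4 | 13.8 | 4.6 |
| 2 | 40.8 | 45.9 | 50.7 | 9.9 | 4.8 |
| 4 | 65.5 | 64.8 | 69.6 | 4.1 | 4.8 |
| 5 | 76.0 | 73.1 | 77.8 | 1.8 | 4.7 |

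The wide spread is confined to Wald against exact at 0 to 2 events.

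**How likely are 0 to 2 events?** The documents give no expected rate, so a range is shown. The probability is 93% at a true rate of 10%, 78% at 1/6, 68% at 20%, 17% at 40% and 5% at 50%. The lower rates suit a DLT reading of the sentence. The higher ones suit any single toxicity of the frequency in Table 4, where fatigue, fever and flu-like symptoms reach 40% to 52% in two of the cited studies.

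**Does the sentence understate uncertainty?** Read as a fixed band of the observed rate ±26 points, it covers a true rate of 10% whenever 3 or fewer events occur, with probability 98.7%. It covers a true rate of 1/6 whenever 4 or fewer occur, with probability 98.5%. Both are above the nominal 90%.

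**The case for a change.** The best case for acting is that the remedy costs one sentence and no subjects, and that the only formula visible in the plan is the wrong one to report. Actual coverage of a nominal 90% Wald interval with n = 10 is 39% at a true rate of 5%, 64% at 10% and 82% at 1/6. Exact limits cover 99%, 99% and 98% at those rates. Naming the method in advance would also remove any choice made after seeing the data.

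These figures are right, and part of the case stands: no method is named, and ±26% would not describe exact limits. But the coverage failure belongs to an analysis the plan does not specify. A sentence saying that the interval will be within a stated margin is a planning statement about what 10 subjects can deliver; it does not commit the report to Wald limits. An analyst faced with 0/10 would not publish an interval from 0% to 0%. Without Wald, the remaining choice moves the upper limit by under 5 points at 0 to 2 events. A late choice also hides little, because the count out of 10 would be reported and any interval can be computed from it. Choosing between exact and Wilson limits is largely preference: exact limits are conservative, while Wilson coverage falls to about 85% at some true rates between 5% and 30%.

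**Conclusion.** No change to the plan is needed. The ±26% is arithmetically correct as the Wald worst case at a 50% rate, and it also bounds the distance of Wilson limits from the observed rate (25.9 points). It does not bound exact limits, which reach 30.7 points from the estimate (half-width up to 27.8). The missing method name is a gap in detail that an analyst fills sensibly.

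The difference of 10 to 26 points in the upper limit requires both that Wald limits are reported, which the plan never says, and that only 0 to 2 events occur, which is likely if the rate concerns DLTs but not if it concerns common toxicities. Between the two methods suited to small counts the difference is under 5 points. The MTD, the escalation and termination rules and the size of the expansion group are all set without this interval. Naming the interval in the study report would be good practice, but it alters no decision in this trial.
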